6.0 Study Investigational Product

Study drug – Sirolimus

Starting dose of 2 mg once daily. Adjusted to maintain drug blood levels of 6-10 ng/ml,

Route – Administered orally

Instructions- Sirolimus can be administered with or without food; however, doses should be administered in a consistent manner. Patients should avoid consuming grapefruit juice while enrolled in the study, as it can interact with the drug mechanism of action.

6.1 Study drug

Six weeks of study drugs will be dispensed at each study drugs visit (and an additional amount for 7 days of study visit window). Investigational product will be stored according the manufacturer's recommendations. The Pharmacy staff will keep a study temperature log for the study drugs. A drug accountability log will be kept by the Pharmacy staff [dispensing information (date and pill number) and drug return information will be recorded].

6.2 Concomitant Medications

Serious drug interactions may occur if GD-sirolimus is co-administration with strong inhibitors of CYP3A4 (such as ketoconazole, voriconazole, itraconazole, telithromycin, or clarithromycin) or inducers of CYP3A4 (such as rifampin or rifabutin).

Participants who meet the inclusion and exclusion criteria for this study and are now enrolled can continue their usual medication/therapy if applicable. All current medications will be reviewed at screening and reviewed for changes at all safety monitoring visit

7.0 Study Outcomes:

7.1 Primary outcome:

Clinical and laboratory adverse event (AE) measures, as per detailed Safety Monitoring: Study participants will be monitored for typical side effects of the study drug, such as gastrointestinal intolerance, infectious symptoms, cough, rash, tremors, etc. Study participants will be monitored for adverse events with history, physical examination (including blood pressure, heart rate, chest exam, etc.) and laboratory studies (electrolytes, renal function, liver function, routine hematology, lipids, drug levels, etc.). Safety monitoring will occur every two weeks by phone and every 1.5 months with clinic visits during treatment periods, and every two weeks by phone during the baseline and follow-up period. Participants will also have daily access to the Study team as needed for any concerns between assessments.

7.2 Secondary outcomes:

Epistaxis data will be collected by PRO-CB using daily diary throughout the 9 months of the study. We will also collect blood sample for biomarkers (specific panel will be determined with the HHT Study team based on biomarkers pilot study analyses) at 4 time points: 3, 4.5, 6 and 9 months

Biopsy tissue sample and blood sample will be sent to two facilities for further analysis; Duke University, USA under the direction of [name] PhD and University of California, San Francisco (UCSF), USA under the direction of [name]. The samples will be in secure storage space in limited access facility until such time as the samples are completely used up or up until study data analysis is completed at which point any remaining samples will be destroyed.

8.0 Data Management

For this pilot study, we plan for 10 participants who complete the 36-week study or at minimum 18 weeks of the study, for the purpose of data analysis.

The following collaborators will be involved in data analysis:

[name], Duke University Medical Center, NC USA

[name] University of California, San Francisco (UCSF), USA

Consortium's Data Management and Coordinating Center (DMCC) at Cincinnati Children's Hospital Medical Center

The Data Management and Coordinating Center (DMCC) Cincinnati, USA, will assign all recruited participants with a participant ID. The link between patient identifying information and database participant ID will only be maintained at the recruiting center. Data will be entered through a web-based system (REDCap) into a central Database developed at the DMCC. Transfer of PHI to the DMCC will be limited as feasible. An appropriate data use agreement is in place to allow secure exchange and confidential processing of PHI by DMCC. A detailed table of relevant fields and their data types and ranges were constructed by combining elements that are in use by the HHT community.

8.1 Sample-size estimate and statistical considerations:

We estimated to have a final sample size of 10 participants for the pilot study. Standard descriptive statistics will be used for reporting the primary and secondary outcome.

8.2 Data collection:

At baseline, comprehensive data regarding patient HHT clinical disease will be collected, including all aspects of disease. In addition, co-morbid disease and baseline medications will be recorded.

9.0 Study Assessment and Procedures

The table of events list (5.4) the assessment time periods

9.1 Tissue Biopsy of available telangiectases:

Excisional punch biopsy of one cutaneous telangiectasia will be performed with 3mm punch biopsy for lesions <3mm in diameter, and with a 5mm punch biopsy for larger telangiectases. The biopsy sample will be taken at the start of study prior to treatment and at end of the 3- month study drug treatment period.

Biopsy will be performed, using standard aseptic technique, and after local injection with lidocaine-epinephrine. We have local experience using this technique and it has been low-risk. Tissue will be fixed in 10% buffered formalin or frozen below 80 degrees Celsius or colder and stained for analysis. Section slides will be prepared, using standard techniques. Tissue will also be stained for angiogenesis, pathway and inflammatory markers (VEGF, Endoglin, ALK1, etc.).

9.2 Serum and plasma collection:

Blood will be drawn for safety measures at each clinic visit and for dose adjustment (see Table of Study Events 5.4). Biomarker samples will be collected at screening, 3, 4.5, 6 and 9 months. Serum/plasma levels will be measured for inflammatory, angiogenic, and BMP9-ALK1-endoglin-Smad1/5/9 pathway markers (9).

10.0 Data and Safety Monitoring

The Study protocol will be reviewed and approved by the Research Ethics Board at St. Michael's Hospital (REB). Participants will be enrolled after the study protocol, consent form and study materials are approved by the REB. Study drug monitoring will occur at each clinic visit and telephone contact. The study team can be reached daily. All current medications will be reviewed at screening and reviewed for changes at all safety monitoring visit.

The study staff will be responsible for documenting and reporting adverse events or serious adverse events. Safety monitoring will occur every 2 weeks by phone during the baseline, study drug treatment and follow-up period. Additionally, safety monitoring will occur at each clinic visits every 6 weeks. Participants will also have daily access to the study team as needed for any concerns between assessments.

10.1 Study drug and adverse event monitoring:

Study participants will be monitored for very common side effects of sirolimus (occur in 10% or more of patients) (10) include:

- a) Abnormal wound healing
- b) Stomach pain, upset and other digestive symptoms, such as diarrhea, nausea, constipation, vomiting
- c) Headache, abnormal vision, shaking (tremor) and some weakness could occur
- d) Acne
- e) Insomnia
- f) Joint, bone or back pain, Swelling of the hands, feet, ankles, or lower legs
- g) Urinary tract infection

Common side effects (occur in less than 9% of patients) include:

- h) Infection (sinusitis, gastroenteritis, influenza, upper respiratory, COVID etc.)
- i) Abnormal bleeding (menstrual, other) or bruising may occur
- j) Dizziness upon standing, feeling anxious and fever or chills may occur
- k) Fluid accumulation/retention
- l) Increased heart rate or heart palpitations
- m) Mouth ulcers or cold sores
- n) Ovarian Cysts
- o) Shortness of breath
- p) Swollen abdomen

Common side effects (occur in less than 1% of patients) include:

- q) Skin cancer (melanoma)

- r) Pancreatitis (inflammation of the pancreas)
- s) Rash and severe allergic reaction including skin reaction may occur

* Women of childbearing potential (pre-menopausal female who are able to become pregnant by any means), will be monitored for pregnancy during follow-up phone visits and at each clinic visit (every six weeks, as a part of the safety lab). Women with a pregnancy lab result for beta hCG Quantitation of > 24 IU/L will be immediately discontinued from study participation and we will seek the participant's permission to monitor the pregnancy and outcome.

Concomitant medications will be monitored; Sirolimus should not be taken with strong inducers and inhibitors of CYP3A or P-glycoprotein (ketoconazole, voriconazole, itraconazole, telithromycin, clarithromycin, or rifampicin, rifabutin)
Pneumonitis (inflammation of the lung tissue) and hyperlipidemia (lipids in the blood) can occur.

Participants are recommended to stop taking study drug and seek immediate medical attention if you develop signs of severe allergic reaction which may include: Chest tightness, Dizziness, Faintness, Rapid heartbeat, Shortness of breath, Skin reaction, Swollen face, lips, or tongue and Wheezing and to contact their doctor immediately if they notice a lump in the neck, armpits, collarbone region, or groin, or unintended weight loss, new moles or any changes in the size, shape, or colour of moles they already have, to monitor for skin cancer.

Vaccination information: Immunosuppressants may affect response to vaccination. Therefore, during treatment with GD-sirolimus, vaccination may be less effective. The use of live vaccines should be avoided”.

10.3 Reporting timeline for adverse events

Adverse events will be reported to Health Canada, the St. Michael's hospital REB and the safety monitoring board.

- i. All reportable Serious Adverse events will be reported by the Investigator within the reporting timelines as per the REB and Health Canada specific guidelines. Including all events that are considered: life-threatening/disabling, results in death of subject, unexpected/unanticipated and other reportable serious adverse events.
- ii. Suspected reportable adverse event will be reported to the safety monitoring board.

11.0 Definition and Standards

11.1 Adverse Event

The International Conference on Harmonization (ICH) Tripartite Guideline define an Adverse Event (AE) as any unfavorable and unintended sign, symptom, or disease temporally associated with the use of a medicinal product, whether or not considered related to the medicinal product.

11.2 Adverse Drug Reaction (ADR)

All noxious and unintended responses to a medicinal product related to any dose should be considered adverse drug reactions. The phrase "responses to medicinal products" means that a causal relationship between a medicinal product and an adverse event is at least a reasonable possibility, i.e., the relationship cannot be ruled out (ICH guidelines).

11.3 Serious Adverse Event (SAE)

Reaction is any untoward medical occurrence that at any dose: results in death, is life-threatening (an event in which the patient was at risk of death at the time of the event), requires inpatient hospitalization or prolongation of existing hospitalization, results in persistent or significant disability/incapacity, or is a congenital anomaly/birth defect (ICH guidelines).

11.4 Unexpected Adverse Event

The nature or severity of which is not consistent with risk information described in the protocol.

11.5 Expected Adverse Event

An event identified in the research protocol as having been previously associated with or having the potential to arise as a consequence of participating in the study

11.5.1 Expected AE: Underlying disease

- a) Clinically significant abnormal lab findings associated with HHT underlying disease.
- b) Medical or surgical procedure associated with HHT underlying diseases.
- c) Symptoms associated with HHT underlying disease.

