Rare Disease Clinical Research Network

Brain Vascular Malformation Consortium

Study Title: **Sirolimus for Nosebleeds in HHT: A Phase II pilot study**

Protocol Number: 200421448

Principal Investigator: **[name] MD MSc FRCPC**

Assistant Professor, University of Toronto
Division of Respiriology, Director of the Toronto HHT Center
St. Michael's Hospital
[name]
[contact]
[contact]

Co- Investigator: **[name] MHSc MD FRCPC**

Assistant Professor, University of Toronto
St. Michael's Hospital, Respiratory and Sleep Medicine
Division of Respiriology
St. Michael's Hospital
[name]
[contact]

Clinical protocol: This protocol is for research purposes only

Phase: II

Drug: Sirolimus (1, 2 or 5mg tablets)

Effective date: Dec 12, 2023

Funded by: National Institutes of Health (NIH)

Synopsis:

This pilot study is to determine the safety and efficacy of oral sirolimus (blood trough level 6-10ng/ml) in patients with HHT that are experiencing moderate or severe epistaxis. The effect of oral sirolimus on epistaxis will be compared to baseline using the Patient-Reported Outcome of cumulative weekly nose Bleeding Duration (PRO-CB). The PRO-CB association with biomarker variability over the duration of the study will be investigated. In the pilot study subjects will be treated with 2mg of sirolimus once daily to obtain a trough level of 6-10ng/ml for 3 months.

Principal Investigator:

[name] MD MSc FRCPC

Assistant Professor, University of Toronto

Division of Respiriology, Director of the Toronto HHT Center

St. Michael's Hospital

[name]

[contact]

Number of study sites: ONE

Study site: St. Michael's Hospital, [name]

Collaborator: (study procedure)

[name], St. Michael's Hospital, Toronto, Ontario, Canada

Collaborators: (sample and data analysis)

[name], Duke University Medical Center, NC USA

[name], University of California, San Francisco

Consortium's Data Management and Coordinating Center (DMCC) at Cincinnati

Children's Hospital Medical Center

Statement of Compliance

The clinical trial will be conducted in compliance with Good Clinical Practice (GCP), the applicable regulatory requirements and according to protocol

All individuals responsible for the design and conduct of this trial have completed Human Subjects Protection Training.

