1.0 Introduction and Background

The most common symptom of the hereditary hemorrhagic telangiectasia (HHT) disease is epistaxis (1). HHT is characterized by vascular (blood vessel) malformations, of the skin and mucus membranes of the nose (telangiectasia), gastrointestinal track, brain, lung and liver (1).

HHT is an autosomal dominant disease which is found in approximately 1 in 5000 individuals (1). Epistaxis affects 90% of adults with HHT, negatively affects quality of life (2, 3) and often causes anemia. Recent topical therapeutics trials have been negative (3) and surgical therapies are invasive and offer only temporary benefit at best. Currently there are no highly-effective or approved systemic therapies for HHT-related epistaxis, but this is an area of active research and development. There is considerable in developing and identifying therapies that target the abnormal biology and mechanisms in HHT, including antiangiogenic therapies, such as bevacizumab (1). Bevacizumab, however, is associated with significant toxicity, costly and administered intravenously.

Over the past few years, there has been considerable new evidence of the pathways involved in HHT disease and related potential therapeutic targets, including the mTOR pathway. Evidence suggests that HHT pathogenesis strongly relies on overactivated PI3K-Akt-mTOR and VEGFR2 pathways in endothelial cells. Ruiz et al (4) recently reported that the mTOR inhibitor, sirolimus, and the receptor tyrosine-kinase inhibitor, nintedanib, synergistically fully blocked, and also reversed, retinal AVMs, in the BMP9/10- immunoblocked neonatal mouse model of HHT. Subsequent unpublished preliminary data demonstrated that sirolimus was more effective than nintedanib at blocking anemia and bleeding in inducible ALK1 knockout HHT mice, and similarly effective to combined sirolimus-nintedanib. As such, sirolimus may provide therapeutic benefit for HHT patients (5). Human studies have shown “low-dose” sirolimus to be low risk and effective as a treatment for other vascular anomalies (6)(7).

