3.1 Purpose

Aims	Endpoint
Specific Aim 1 To determine the safety of a 6-10ng/ml dose oral sirolimus in patients with HHT, with moderate or severe epistaxis.	Clinical and laboratory adverse event (AE) measures, as per detailed Safety Monitoring:
Specific Aim 2A: To measure the effect of a 6-10ng/ml dose of oral sirolimus on epistaxis in HHT patients, compared to baseline epistaxis	Epistaxis will be measured using the Patient-Reported Outcome of cumulative weekly nose Bleeding Duration (PRO-CB), compared to baseline PRO-CB, obtained from daily epistaxis diary.
Specific Aim 2B: To characterize PRO-CB in HHT patients with moderate to severe epistaxis.	PRO-CB using daily diary throughout the 9 months of the study.
Specific Aim 3: To explore biomarkers variability over time, on/off therapy and association with PRO-CB.	We will collect plasma for biomarkers (specific panel will be determined with the HHT Study team which may include the following: ANG2 sICAM1 PIGF TSP2 sVEGFR2, BMP9 IL6 SDF1 sVCAM1 sVEGFR3, sCD73 sIL6R TGFβ1 VEGF, sENG OPN TGFβ2 VEGF-C, GP130, PDGF-AA, sTGFβR3, VEGF-D, HGF PDGF-BB, TIMP1, sVEGFR1 (Wetzel-Strong et al. Orphanet J Rare Dis (2021) 16:372)

4.0 **Research Plan**

Sirolimus is a potential therapy of interest in HHT, The primary outcome is the reduction of epistaxis (minutes per week), as adults with HHT are almost universally affected by epistaxis and it is known to impair quality of life (3). The study aims to investigate subjects with moderate to severe epistaxis, using sirolimus target trough 6-10 ng/ml for 3 months.

4.2 Study Participants:

The study will include a maximum of 20 enrolled participants with a final target of 10 subjects who entirely or partially complete study drug intervention. Participants will be recruited from the Toronto HHT Center, at St. Michael's Hospital, and through the Rare Diseases Network website (<https://www1.rarediseasesnetwork.org/cms/bvmc/Get-Involved/Studies>).

The primary outcome for the trials will be the reduction of epistaxis severity (minutes of bleeding per week).

4.3 Inclusion and Exclusion Criteria:

4.3.1 Inclusion criteria:

- a) Age \geq 18 years
- b) Clinical HHT diagnosis (8) or genetic diagnosis of HHT
- c) Epistaxis at least 15 min per week.
- d) COVID-19 Vaccine (2 doses)
- e) Ability to give written informed consent, including compliance with the requirements of the study.

4.3.2 Exclusion criteria:

- a) Allergy/intolerance to the study drug or related agents

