5.2 Study Design Discussion

All participants will receive 3-month course of study drug

The collaborating doctor ([name]) will advise on dose adjustment to maintain a drug blood level of 6-10 ng/ml.

A medical history and physical examination will be performed at all clinic visits.

5.2.1 Specific study drug dosing:

Sirolimus starting dose of 2 mg once daily, orally adjusted as need to maintain drug blood levels of 6-10 ng/ ml

The first dose will be given at the week 12 visit and participants will be observed for 30 min

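### Eligibility sets no stability condition for other bleeding-directed therapy, so in an own-baseline comparison a therapy that starts, stops or wears off can mimic or mask a sirolimus effect

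*Protocol*

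**What the plan says.** - **Eligibility (Protocol 4.3).** The only criterion on nosebleeds is "Epistaxis at least 15 min per week" in 4.3.1. The other inclusion and exclusion items cover age, diagnosis, vaccination, consent, drug tolerance, general health, laboratory values, pregnancy and contraception, immune status, malignancy, lipids and product-monograph contraindications. None mentions nasal procedures, antiangiogenic drugs or any other treatment for bleeding.
- **Background therapy (6.2).** Enrolled participants "can continue their usual medication/therapy if applicable". The drugs warned against, here and in 10.1, are those that interact with sirolimus. That is a safety rule and does not stabilise bleeding therapy. Medications are reviewed at screening and checked for changes at safety visits (6.2, 10.0).
- **Other therapies (1.0).** On surgery: "surgical therapies are invasive and offer only temporary benefit at best". The same section names bevacizumab as an antiangiogenic directed at HHT mechanisms.
- **Efficacy comparison (3.1, Aim 2A).** "To measure the effect of a 6-10ng/ml dose of oral sirolimus on epistaxis in HHT patients, compared to baseline epistaxis". Under 5.2, "All participants will receive 3-month course of study drug", so there is no concurrent control. Section 5.3 gives three months each of baseline, treatment and follow-up.
- **Size and analysis (8.1).** "We estimated to have a final sample size of 10 participants for the pilot study", with descriptive statistics.
- **Expected adverse events (11.5.1).** One class is "Medical or surgical procedure associated with HHT underlying diseases".

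**The concern.** In a single-arm before-after comparison, nothing separates the study drug from any other cause of change over the same weeks. Section 1.0 supplies two such causes: surgery whose benefit fades, and drugs that act on the disease. A participant treated shortly before screening can enter if bleeding still meets the threshold. If that benefit fades after baseline, it hides a sirolimus effect. A therapy begun late in baseline or during treatment looks like one.

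The result is meant to help plan a randomised, placebo-controlled trial (1.0), so a distorted change would carry into that planning. Sections 4.0 and 4.2 also call reduction in epistaxis the primary outcome, while 1.0 and 7.1 give that place to safety. That conflict is a separate matter, but it means the epistaxis change may be read as a headline result.

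**Working it through.** The protocol states no figure on this point: n = 10 comes without an effect size, standard deviation, alpha or power. What follows is illustration. From the protocol I take 10 participants (8.1), about 12 baseline and 12 treatment weeks (5.3, 5.4), and own-baseline comparison (3.1). The proportional effect e of another therapy and the chance p that a participant is affected are assumptions.

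**1. Constant therapy.** Suppose another therapy multiplies bleeding by c in both periods and sirolimus reduces it by a fraction s. The on-drug to baseline ratio is cB(1 − s)/(cB) = 1 − s. The other therapy drops out.

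**2. Therapy acting only during treatment, no sirolimus effect, equal baselines B.** With k of 10 affected, the on-drug mean is B(10 − ke)/10, a relative fall of ke/10.

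| k | e = 0.3 | e = 0.5 | e = 0.7 |
|---|---|---|---|
| 1 | 3% | 5% | 7% |
| 2 | 6% | 10% | 14% |
| 3 | 9% | 15% | 21% |

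If the effect covers only 6 of the 12 treatment weeks, each entry halves; for k = 1 the range is 1.5% to 3.5%.

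**3. Unequal baselines.** If one affected person contributes a share w of the group's baseline minutes, mean or total minutes fall by w × e. A person bleeding twice the mean has w = 2/10, giving 0.2 × 0.3 = 6% to 0.2 × 0.7 = 14%. This depends on the summary, which 8.1 does not fix. A mean of individual percentage changes moves by e/10 whatever w is, and a median would generally move less.

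**4. Benefit that wears off.** If one participant is suppressed by e at baseline and back at B on treatment, the baseline mean is B(10 − e)/10 and the on-drug mean is B. The apparent rise is e/(10 − e): 0.3/9.7 = 3.1% to 0.7/9.3 = 7.5%. A sirolimus benefit of about that size would be hidden.

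**5. How often.** The protocol gives no rate. If each participant independently has chance p of another bleeding therapy starting, stopping or wearing off over the nine months, the chance that at least one of 10 is affected is 1 − (1 − p)^10.

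| p | at least 1 of 10 | at least 2 of 10 |
|---|---|---|
| 5% | 40% | 9% |
| 10% | 65% | 26% |
| 20% | 89% | 62% |
| 30% | 97% | 85% |

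Not every such change falls between baseline and treatment, so these overstate how often Aim 2A itself is affected.

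**6. What is already recorded.** Medication changes and adverse events are reviewed about every two weeks (7.1, 10.0), and baseline medications and HHT disease data are collected (8.2). The diary text in 5.3.1 asks for duration and intensity of each bleed. No section expressly asks for dates of nasal procedures or of changes in bleeding therapy. The diary form in the appendices could not be read in the text available, so nothing here rests on its layout.

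**The case against.** The case on the other side has real weight.

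- **Existing contacts catch much of this.** Changes in medication would largely be noticed, and procedures logged as adverse events would be documented. This stands. A reader might infer that such information goes uncollected; the protocol does not support that. What is missing is an explicit, dated record tied to bleeding therapy.
- **Section 11.5.1 proves little.** A reader might take it as evidence that nasal procedures are expected during the study. It only defines which adverse events count as expected. It covers procedures for HHT in any organ, and 1.0 lists gut, brain, lung and liver as well as nose. It gives no frequency. The point rests on 6.2 with 4.3 and 1.0.
- **Being on another therapy is not itself a bias.** This stands, by step 1. Section 6.2 also speaks of usual therapy, which does not naturally describe a newly started antiangiogenic. But no rule addresses starting one, and a recent procedure can fade without anyone changing anything.
- **The design helps.** Someone whose bleeding is well controlled may miss the entry threshold. Daily diaries through baseline and follow-up can reveal a trend, a sudden change or a missing rebound. These features aid detection; they do not remove the bias.
- **The stakes are modest.** This is a small descriptive pilot, and section 12.0 accepts that no effect may be seen. This tempers the priority.

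**Conclusion.** The point holds in a limited form. The protocol admits participants without asking that bleeding-directed therapy be stable, and its only efficacy contrast cannot separate a change in such therapy from sirolimus. The direction is not fixed: the change may mimic or mask a benefit.

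Under equal baselines, and with one of 10 participants changing by 30-70% for another reason throughout treatment, the group mean shifts by 3-7%, and by more for a heavy bleeder if minutes are averaged or pooled. The frequency is unknown. A much larger distortion could be constructed by assuming that bleeding stops entirely in a very heavy bleeder and that group minutes are pooled, but the protocol supports none of those assumptions.

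The entry condition belongs in the protocol, because an analysis plan cannot add one afterwards. How affected weeks are then summarised may properly be left to the SAP, and its absence here is no finding. This is a cheap, worthwhile improvement to the efficacy aim and does not invalidate the pilot.

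**What to change.** 1. **Section 4.3:** add that bleeding-directed therapy (nasal procedures, antiangiogenic or other systemic bleeding agents) has been stable for a defined period before screening, with no elective change planned through the study. The investigators decide which therapies count and how long the period is. State that care a participant needs during the study is not restricted.
2. **Sections 6.2 and 10.0:** at the existing two-weekly contacts, explicitly record the date of each nasal procedure and each start, stop or change of bleeding therapy. This extends the present medication and adverse-event review and lets affected PRO-CB weeks be identified.

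The cost is one eligibility line and one item on an existing contact form. The downside is slightly slower recruitment.
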